1.3 Etiology and Burden of ILIs in Mexico

During 2009-2010, a new influenza virus (A/California/07/2009 H1N1) spread worldwide causing the first flu pandemic in more than 40 years. Because of the significant fatality rates and the fact that Mexico City was the epicenter of the earliest reported cases, the Mexican Ministry of Health and NIAID collaborated to establish the LaRed network. LaRed's observational cohort study of ILIs in Mexican adults and children has over 5600 subjects over 4 years (data as of July 2014). Analysis of the first years data found that, in addition to influenza which accounted for 24% of viral isolates, rhinovirus, coronavirus, RSV, and adenovirus contributed significantly to the burden of disease, accounting for 25%, 14%, 10%, and 9% of all viral isolates respectively.¹² Similar results are seen in the 3 year data (unpublished). For severe (hospitalized) disease, similar viruses caused disease (see Table 2). While NTZ is not thought to treat rhinovirus, it is thought to be efficacious in treating adenovirus, coronavirus, influenza, parainfluenza, and RSV, and likely efficacious in treating mixed infections. Additionally, in the Phase 2b-3 data there was efficacy in the “negatives” (pointing to likely infectious agent). Taken together, these categories make up 76% of hospitalized ILI (i.e., SARI) patients that LaRed has been able to enroll previously.

Table 2: Pathogen distribution in hospitalized ILI cases in LaRed over 3 years, by age group

Pathogen	Children ≥ 2 to <12 years old	Adults ≥ 12 years old	Total	%Total
Adenovirus	6	24	30	2.2
Bordetella pertussis	2	5	7	0.5
Coronavirus	9	55	64	4.7
Coronavirus 229E	2	18	20	
Coronavirus NL63	3	20	23	
Coronavirus OC43	4	17	21	
Chlamydophila pneumoniae	0	0	0	0.0
Influenza	21	112	133	9.7
Influenza A	2	10	12	
Influenza A H1N1	7	34	41	
Influenza A H3N2	5	44	49	
Influenza B	7	24	31	
Legionella pneumophila	0	0	0	0.0
Metapneumovirus	17	34	51	3.7
Mycoplasma pneumoniae	2	18	20	1.5
Parainfluenza	15	29	44	3.2
Parainfluenza 1	4	2	6	
Parainfluenza 2	5	8	13	
Parainfluenza 3	4	9	13	
Parainfluenza 4	2	10	12	
Rhinovirus	40	207	247	18.0
RSV	44	35	79	5.7
RSV A	37	31	68	
RSV B	7	4	11	
Mixed	43	107	150	10.9
Negative	54	497	551	40.0
Total	253	1,123	1,376	

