3 INVESTIGATIONAL PLAN

3.1 Research question

Does treatment with NTZ improve the outcome of subjects with SARI caused by respiratory viruses?

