## Analysis Plan

### Subject Populations

Here we give the definitions for the populations that will be referred to for different analyses.

- Enrolled: all subjects that signed consent
- Intention to Treat (ITT) population: per protocol defined as all participants who are randomized and received at least 1 dose of the study drug, and for analysis the treatment group will be assigned as randomized.
- ITT age subgroups (only on specified analyses):
  - Adults  $\geq$  18 years
  - Children aged  $<18$  years
- ITT pediatric formulation subgroups (only on specified analyses; may be omitted depending on the number of subjects enrolled in each pediatric subgroup):
  - Children  $\geq$  13 years and  $<18$  years (children that take the adult tablet formulation)
  - Children aged  $<13$  years (as this is the age for pediatric formulation)
- ITT virology subgroups (only on specified analyses):
  - Influenza A or B
    - Influenza A
    - Influenza B
  - RSV
  - Human Metapneumovirus
  - Rhinovirus/Enterovirus
  - Adenovirus
  - Mycoplasma pneumoniae
  - Chlamydophila pneumoniae
  - Legionella pneumophila
  - Bordetella pertussis
  - Parainfluenza
  - Bocavirus
  - Coronavirus

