## 11. Primary Endpoint (ITT, ITT age subgroups, ITT pediatric formulation subgroups, ITT virology subgroups)

Table to show the completeness of the primary endpoint should include number (%) with [14.2.2]:

- Complete data (Day of hospitalization and discharge or death)
- Incomplete data (missing day of hospitalization or discharge/death)

The following table and figure provide descriptive statistics of the primary endpoint. The table and figures should impute values of 28 days for patients who died and should censor patients with missing discharge date at the time of last follow up.

- Figure: Kaplan-Meier plot of time to hospital discharge/death (only ITT and ITT age subgroups)
- Table: with the following estimates from the Kaplan-Meier curves- 25th, 50th and 75th percentile along with min and max values in hours [14.2.3.1.x]

- The between group difference in median time to discharge will be used to estimate the treatment effect and will be reported along with a 95% two-sided confidence interval.
- Additionally, data from median, min, max converted to “days, hours”
- The p-value for the 2 group comparison of the primary endpoint analysis will be performed using the Shaw-Fay method as described in appendix 1.
- Sensitivity analyzes to exam effect of missing death or discharge data. (only ITT and ITT age subgroups)
  - Figure with Kaplan-Meier curves and Shaw-Fay p-values on the ITT only where missing death or discharge dates are imputed in the placebo group as censored at the time of last follow up and in the experimental group are imputed as events at day 28.
  - Figure with Kaplan-Meier curves and Shaw-Fay p-values on the ITT only where missing death or discharge dates are imputed in both groups as events at day 28.
  - For any imbalance seen in baseline characteristics ( $p < .05$ ) perform a cox proportional hazards model with deaths receiving event times of 28 days. Missing discharge dates will be censored at last follow up time.

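### On clinical endpoints the SAP defines no virus-positive or pathogen-negative group; it gives 14 mostly tiny pathogen groups a separate p-value each, with no interaction test

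*SAP*

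**What the plan says.** - **Question.** Protocol 3.1 asks: "Does treatment with NTZ improve the outcome of subjects with SARI caused by respiratory viruses". The hypothesis in 3.2 is framed the same way. The primary objective (2.1) is wider and covers treatment of SARI as such.
- **Rationale.** Protocol 1.2.5 reports a benefit in outpatients with no virus identified (p=0.0208) and no apparent effect in those with rhinovirus. Section 1.3 builds on this: "Additionally, in the Phase 2b-3 data there was efficacy in the" negatives. It then groups the negatives with mixed infections and the viruses thought susceptible, as 76% of hospitalised cases, and leaves rhinovirus out.
- **Subgroups.** The SAP's Subject Populations section defines "ITT virology subgroups (only on specified analyses") and lists 14 groups: influenza A or B, influenza A, influenza B, RSV, metapneumovirus, rhinovirus/enterovirus, adenovirus, four bacteria, parainfluenza, bocavirus and coronavirus. There is no any-virus, mixed or no-pathogen group. Only the pediatric formulation subgroups may be omitted when numbers are small.
- **Analysis.** SAP section 11 is headed "Primary Endpoint (ITT, ITT age subgroups, ITT pediatric formulation subgroups, ITT virology subgroups"). Its Kaplan-Meier figure and sensitivity analyses are limited to the ITT and age subgroups. The median difference with its interval, and the test, are not: "The p-value for the 2 group comparison of the primary endpoint analysis will be performed using the Shaw-Fay method as described in appendix 1". Section 12 (secondary endpoints) covers the ITT and age subgroups only, apart from Day 3 viral clearance, which is restricted to patients with virus on Day 0.
- **Protocol's subgroup plan.** Section 9.2 calls repeating the primary analysis in influenza-positive patients important, and names age and pathogen type as other subgroups.

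**The concern.** The two contrasts that the rationale rests on are virus-positive versus negative, and rhinovirus versus the viruses thought susceptible. The SAP prespecifies neither for a clinical endpoint. An estimate of the effect on hospital stay in confirmed viral SARI would therefore be post hoc.

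What is planned instead is a set of separate p-values in small groups. A significant result in one group and not in another does not show that the effect differs between them, and no interaction test is planned that would. With no minimum size and no multiplicity rule, an isolated small p-value could be read as pathogen-specific efficacy. No rule says where a patient with two pathogens belongs.

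**Working it through.** **1. Reproduce the plan's sample size.** Inputs from Protocol 9.2: log-day means 1.83 and 1.58, log SDs 0.66 and 0.76 (Delta = 1.25 days), two-sided alpha .05, unequal-variance t-test. With n per arm, SE = sqrt((0.66² + 0.76²)/n) = sqrt(1.0132/n) and noncentrality = 0.25/SE. At n = 129, SE = 0.0886, noncentrality = 2.82 and power = 80.2%. The stated total of 258 is reproduced, so the same calculation is used below.

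**2. Expected group sizes.** Each is the Table 2 count (Protocol 1.3) divided by 1,376, times 290.
- Single viruses: 30 + 64 + 133 + 51 + 44 + 247 + 79 = 648. Adding 150 mixed gives 798 (58.0%), so 798/1,376 × 290 = 168. At the protocol's 60% (Summary) or 70% (section 4.1) it is 174 or 203.
- Negatives: "Negative 54 497 551 40.0" gives 551/1,376 × 290 = 116. At 30% it is 87.
- Any virus other than rhinovirus alone: 798 − 247 = 551, also 116. This assumes that every mixed infection includes another virus.
- Rhinovirus: "Rhinovirus 40 207 247 18.0" gives 247/1,376 × 290 = 52.
- The 76% in section 1.3 checks: 30 + 64 + 133 + 44 + 79 + 150 + 551 = 1,051, and 1,051/1,376 = 76.4%.

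**3. Power for 1.25 days.**

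| Group | Expected n | Power |
|---|---|---|
| Any virus | 168 / 174 / 203 | 62% / 63% / 70% |
| No pathogen | 116 / 87 | 47% / 37% |
| Rhinovirus | 52 | 24% |
| Influenza A or B | 28 | 15% |
| Influenza A | 21.5 | 12% |
| RSV | 17 | 10% |
| Coronavirus | 13 | 9% |
| Metapneumovirus | 11 | 8% |
| Parainfluenza | 9 | 8% |
| Influenza B; adenovirus | 6.5; 6 | 6% each |
| *M. pneumoniae* | 4 | 6% (t-test; see step 4) |
| *B. pertussis* | 1.5 | not estimable |
| *C. pneumoniae*; *L. pneumophila* | 0; 0 | none |

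Bocavirus is not in Table 2. If each mixed infection is taken as two pathogens in proportion (a rough assumption), rhinovirus rises to about 76 (about 32%), influenza to 41 (19%) and RSV to 24 (13%).

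**4. Which groups can reject.** The smallest two-sided permutation p with a and b patients per arm is 2/C(a+b, a). It is 2/6 = 0.33 at 2 v 2, 2/20 = 0.10 at 3 v 3, 2/35 = 0.057 at 3 v 4 and 2/70 = 0.029 at 4 v 4. At the expected counts *M. pneumoniae*, *B. pertussis*, adenovirus and influenza B cannot reach .05. Six disjoint groups can: rhinovirus, influenza, RSV, coronavirus, metapneumovirus and parainfluenza.

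**5. Chance of at least one false positive.** For six independent tests, 1 − 0.95⁶ = 26%. Rank tests in small groups are conservative. Exact sizes at 26/26, 14/14, 8/9, 7/7, 5/6 and 4/5 per arm are 4.9%, 5.0%, 4.6%, 3.8%, 3.0% and 3.2%, which combine to about 22%.

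**6. What an interaction test could show.** Suppose the full 0.25 log-day effect in 168 virus-positive patients and none in 116 negatives. SE = sqrt(1.0132/84 + 2 × 0.66²/58) = 0.165, z = 0.25/0.165 = 1.52, and power is about 33%. The interval for the difference will say more than the p-value.

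**The case against.** **The all-comers design is deliberate.** The primary objective and sample size cover all hospitalised SARI, and section 1.3 counts the negatives among patients thought likely to respond. This stands. A reader might infer that the primary analysis addresses the wrong population, but section 2.1 does not support that. A virus-positive group would be one secondary subgroup, and the protocol does not name it.

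**Virus-positive patients are analysed.** A reader might infer that they and the negatives are left out altogether. They are not: both are in the ITT analysis, and SAP section 12 pools the virus-positive for Day 3 clearance. The gap is confined to clinical endpoints.

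**The multiplicity is easy to overstate.** Fourteen independent tests would give 1 − 0.95¹⁴ = 51%, and that figure is tempting. It counts two nested groups, two with no cases in Table 2 and several too small to reject. The worry about chance positives therefore applies to groups of about nine patients or more.

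**The SAP follows the protocol.** Section 9.2 names influenza-positive and pathogen type, so dropping every pathogen p-value would remove an analysis the protocol calls important. This also stands, and the fix keeps that analysis.

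**The groups need not be sole infections.** The SAP does not restrict them to patients with one pathogen, and influenza, parainfluenza and coronavirus each pool types. This is correct, and it exposes the missing rule for mixed infections (10.9% of Table 2).

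**Conclusion.** The point holds as a cheap improvement to secondary subgroup reporting; the primary analysis is not in error. For clinical endpoints the SAP prespecifies neither the virus-positive group that the research question describes nor the negatives that the rationale cites. It spends its subgroup p-values on groups that have at most about 24% power for the planned effect (about 32% with coinfections counted), and several of them cannot reject at all. The pooled groups would have 62% to 70% and 37% to 47%.

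These figures assume that the Table 2 mix carries over. That cohort is earlier and starts at age 2, while the trial enrols from 12 months. They also assume that the 1.25-day effect and its variance apply within each group, that arms split evenly, that mixed infections include a virus, and that all 290 contribute data. The 30% negative share treats everyone without a virus as negative; bacteria-only cases are 27/1,376 = 2% of Table 2. At 258 patients the virus-positive and negative groups fall to about 150 and 103, with power of about 57% and 42%. The 26% assumes independent tests.

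**What to change.** Before unblinding, amend the SAP (Subject Populations and section 11):

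1. Add three groups, labelled as secondary subgroups of the all-SARI ITT analysis: any virus on Day 0; any virus other than rhinovirus/enterovirus alone; no pathogen detected.
2. State how mixed infections are assigned, and where bacteria-only and untested patients go.
3. Report the treatment effect with a 95% CI in each group, and a treatment-by-group interaction test between non-overlapping groups, for example virus-positive versus pathogen-negative. Name the effect measure and the test. Say that power for interaction is low.
4. Keep the influenza-positive analysis with its p-value, as Protocol 9.2 intends.
5. Show the other pathogen groups descriptively, and record that this is how the protocol's pathogen-type subgroup is handled.

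The cost is SAP wording and a few table rows. Day 0 PCR is already collected, and section 12 already uses virus on Day 0 as a restriction. The p-values for the individual pathogens other than influenza are given up.

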## Table and Figure presentation

Results in figures and tables will be presented

- all subjects (total)
- by randomized arm

Number in brackets [] represents corresponding table number

### 1. Accrual, eligibility violations and exclusions from analyses (Enrolled)

- Table: Number enrolled: overall and by month/year and by institution. Dates of first and last subjects screened. [14.1.1.1]
- Figure: Number enrolled, by month/year
- Table: Screen failures, and number of subjects for each inclusion and exclusion criteria. [14.1.1.2]
- List: description of subjects screened and excluded from the ITT: Randomized arm, study drug received (yes or no), site, age, subject ID, subject's study status (completed study, died, discontinued early from study), reason for exclusion.

### 2. Accrual, eligibility violations and exclusions from analyses (ITT and ITT age subgroup)

- Table: Number randomized: overall and by month/year and by institution. Dates of first and last randomizations. [14.1.1.3]
- Figure: Number randomized, by month/year. Note the date of data lock for interim efficacy analysis.
- List: Description of violations of eligibility criteria among subjects randomized: Randomized arm, study drug received (yes or no), site, age, subject ID, subject's study status (completed study, died, discontinued early from study), reason for violation as noted by site.

### 3. Selected characteristics of participants at baseline (Day 0) (ITT)

Baseline is defined as the last observation prior to study drug administration. P-values using the test of means for continuous variables, test of proportions for binary endpoints or chi-square tests for categorical endpoints

- Demographics [14.1.3]
  - Table: Age (median, 25th and 75th percentile, mean, min, max)
  - Table: number randomized by age group (<2 years, ≥2 years to <8 years, ≥8 years to <13 years, ≥13 years to <18 year, ≥18 years to <65 years, ≥65 years).
  - Sex (%)
  - Self-reported NIH race/ethnicity (%)
  - Medical History (occurring in 5% or more of the study population)
  - BMI for adults age ≥18 years
  - Z score for age <18 years
  - Smoking History
- Baseline Disease Characteristics [14.1.4.1, 14.1.4.2, 14.1.4.3, 14.1.4.4]
  - Influenza vaccination history (categorical - vaccinated the season of enrollment)
  - Confirmed pathogen by multiplex PCR (i.e. Respifinder®). Include totals for pathogen type (e.g. all influenzas), and for each strain (e.g., H1N1 influenza)
  - Days since onset of symptoms (onset of symptoms to randomization).
  - Days since onset of symptoms to first dose.
  - SaO2

- Severity of illness score
  - Sequential Organ Failure Assessment (SOFA) score for subjects  $\geq$  24 months of age
  - Tal bronchiolitis score for subjects  $<$  24 months of age
- Charlson comorbidity index.
- Chronic oxygen use
- Oxygen requirement (yes/no)
- ICU requirement (yes/no)
- Presence of Complications
  - Pneumonia (clinical diagnosis supported by radiographic data)
  - Respiratory failure requiring mechanical ventilation (documentation of mechanical ventilation)
  - ARDS (clinical diagnosis supported by radiographic data)
  - Sepsis (clinical diagnosis)
  - Bronchiolitis (clinical diagnosis)
- Presence of symptoms for each of the following (defined as 2 or 3 = symptoms present):
  - Cough
  - Sore throat
  - Fatigue
  - Headache
  - Myalgia
  - Rhinorrhea
  - Nausea
  - Vomiting
  - Diarrhea
- CBC with differential white cell count (to include neutrophil, lymphocyte, and eosinophil percentages), hemoglobin, hematocrit, and platelets
- Blood chemistries (creatinine, ALT/GPT, AST/GOT, total bilirubin, LDH, CRP)
- Global Assessment
  - Adult
    - Overall question
    - Function question
  - Pediatric
    - Activity
    - Diet

#### 4. Study status of participants and loss to follow-up (ITT)

- Table: Number (%) for the following categories: [14.1.2]
  - Off study: completed study (completed day 28 visit or died prior to 28 days of follow-up)
  - Off study: died
  - Off study: lost to follow-up before completing 28 days of follow-up
    - subcategories for each of the reasons for early discontinuation
- List: subjects lost of follow-up and last date

#### 5. Study drug receipt (ITT) [14.2.1]

- Table showing number (%) in following categories

- Full planned treatment
- Partial treatment (by doses received – 9,8,7...etc.)
- Listing of subjects that did not receive full planned treatment: subject ID, site, age, at request of study team, reason for not receiving full planned treatment.

## 6. Concomitant medications (ITT)

- Anti-influenza antivirals during first 5 days [14.3.4.1]
  - Table of influenza antivirals taken (y/N)
  - If yes: number (%) for each specific drug
- Antibiotic during first 5 days [14.3.4.2]
  - Table of if antibiotics taken (Y/N)
  - If yes: number (%) for each specific drug
    - Grouping by family
    - Grouping by pathogens targeted (gram positive, gram negative, atypical, anaerobic)
- (note – groupings will be decided after study is closed to new enrollment by looking at pooled data but before study unblinding)*
- Systemic steroids during first 5 days [14.3.4.3]
  - Table of systemic steroids taken (y/N)
  - If yes: number (%) for each specific drug

## 7. Mortality (ITT and ITT age subgroups)

- Table: [14.3.3]
  - number (%) total deaths
  - deaths in first 5 days
- List of deaths: Randomized arm, days from randomization to death, subject ID, site, age, primary cause of death, relatedness to study intervention. Sort by randomized arm, days from randomization to death and subject ID.
- Figure and Analysis: Kaplan-Meier plot of time from randomization to death (censoring at 28 days if completed follow-up, or at date of last contact if lost to follow-up prior to 28 days), with associated table showing: number censored and number (%) dying, median time to death and associated 95% confidence interval; p-value from log-rank test. The estimated hazard ratio and associated 95% confidence interval comparing randomized arms will be obtained using a proportional hazards model applied to the times of death with censoring as above.

## 8. Serious Adverse Events (ITT)

- Table: [14.3.2.1] Number (%) of subjects with an SAE by MedDRA System Organ Class (SOC) and Preferred Term (PT); number (%) of subjects with any SAE. In these tables, subjects with SAEs will be counted (e.g. counting a subject with multiple SAEs with the same PT only once for that PT).
- Table: [14.3.2.2] Number of SAEs by MedDRA System Organ Class (SOC) and Preferred Term (PT); number (%) of SAEs. In these tables, SAEs will be counted (e.g. counting multiple SAEs with the same PT within the same subject).

- List of SAEs: Randomized arm, days from randomization to first SAE experienced by a subject, subject ID, site, age, days from start of study drug to SAE, SAE (MedDRA SOC and PT, and verbatim description), severity grade, relatedness to study intervention, outcome (sort by randomized arm, subject ID, MedDRA SOC and PT and, if a subject has multiple SAEs, days from randomization to SAE). This listing will include any SAE that occur after day 28 and are reported.
- Listing of SAE after enrollment (informed consent) and not included in the ITT

## 9. Adverse Events (ITT)

- Table: [14.3.1.1] Number (%) of subjects with an AE by MedDRA System Organ Class (SOC) and Preferred Term (PT) and severity grade; number (%) of subjects with any AE. In this table, subjects with AEs will be counted (e.g. counting a subject with multiple AEs with the same PT only once for that PT).
- Table: [14.3.1.2] Number of AEs by MedDRA System Organ Class (SOC) and Preferred Term (PT) and severity grade; number (%) of AEs. In this table, AEs will be counted (e.g. counting multiple AEs with the same PT within the same subject).
- List of AEs: Randomized arm, days from randomization to first AE experienced by a subject, subject ID, site, age, days from start of study drug to AE, AE (MedDRA SOC and PT, and verbatim description), severity grade, relatedness to study intervention, outcome (sort by randomized arm, subject ID, MedDRA SOC and PT and, if a subject has multiple AEs, days from randomization to AE). This listing will include any AE that occur after day 28 and are reported.
- Listing of AE after enrollment (informed consent) and not included in the ITT

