5.1 Blinding, Randomization, Stratification, and Treatment Assignment

Treatment kits will be blinded and numbered. The two treatment arms are not distinguishable at the site. Therefore the study team, the pharmacy, and the monitors will be blinded.

The randomization scheme will be prepared by the sponsor. Those unblinded are limited to the statistician not involved with the study who generated the randomization code, and the pharmaceutical group that packaged the study drug. The Data and Safety Monitoring Board (DSMB) will have access to the unblinding code in a sealed envelope.

The study will remain blinded until after the last subject enrolled has completed the last follow-up visit and all data queries have been resolved. The study will then be unblinded for analysis.

Randomization will be built into the treatment kit order at each site (i.e., kit #101 may be NTZ or PCB depending on the randomization scheme).

Randomization will be stratified by sites and by adult and pediatric (<12 years). Randomization will occur in blocks of 4. Each site will receive study drug in multiples of 4, thus ensuring randomization is balanced by site.

Subjects who meet all criteria for enrollment will be assigned the next study kit at a site. Kits will be assigned in a consecutive manner starting with the first kit number in the block at each site.

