5.2 Study Regimens and Administration

The sponsor will supply each site with study agent near the time of site activation. Each randomized subject will receive a study drug kit consisting of 5 days of treatment. The site pharmacy will distribute the study kits. The method of supplying study agent to hospitalized subjects will be customized at each site.

Subjects take the medication twice daily, with food, and each dose will consist of the following:

Adults and Children 12 years and older:

The active formulation for this study is a yellow, film-coated tablet that contains 300 mg NTZ plus standard excipients. This is an extended release formulation of licensed NTZ. This formula provides a mean AUC_t 29 $\mu\text{g}^*\text{hr}/\text{mL}$ and mean C_{\min} (12 h) 0.8 $\mu\text{g}/\text{mL}$.

The placebo tablet will have the same appearance and inactive ingredients as the active tablet.

Group 1 (NTZ): 2 NT-300 mg tablets orally BID x 5 days.

Group 2 (Placebo): 2 placebo tablets orally BID x 5 days.

Children younger than 12 years:

The formulation for children younger than 12 years is the currently licensed suspension of nitazoxanide (Alinia®), or matching placebo.

Group 1 (NTZ):

4-11 years: 10 mL oral suspension (200 mg NTZ) every 12 hours x 5 days

1-3 years: 5 mL oral suspension (100 mg NTZ) every 12 hours x 5 days

Group 2 (Placebo):

4-11 years: 10 mL oral suspension (placebo) every 12 hours x 5 days

1-3 years: 5 mL oral suspension (placebo) every 12 hours x 5 days

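### AE and SAE tables pool the under-12 suspension group with the tablet group, so no planned table gives incidence for the smaller paediatric regimen

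*SAP*

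**What the plan says.** **Population for the AE and SAE tables.** The SAP headings are "8. Serious Adverse Events (ITT" and "9. Adverse Events (ITT". Neither names a subgroup. The SAP's general rule on tables and figures is to present all subjects and each randomised arm.

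**When subgroups apply.** The SAP's Subject Populations section introduces "ITT age subgroups (only on specified analyses", split at 18 years. A separate paediatric formulation subgroup splits at 13 years, with the reason given as "as this is the age for pediatric formulation". It too is limited to specified analyses and may be dropped if numbers are small. Mortality (section 7), laboratory values (section 10) and secondary endpoints (section 12) name the age subgroups. The formulation subgroup is named in one place only: "11. Primary Endpoint (ITT, ITT age subgroups, ITT pediatric formulation subgroups, ITT virology subgroups".

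**What the arms contain.** Protocol 5.2 states: "The formulation for children younger than 12 years is the currently licensed suspension of nitazoxanide". The suspension dose is 100 mg at 1 to 3 years and 200 mg at 4 to 11 years, twice daily for 5 days. From 12 years the dose is two 300 mg extended-release tablets twice daily for 5 days. Placebo matches each formulation. Protocol 5.1 states: "Randomization will be stratified by sites and by adult and pediatric (<12 years".

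**What else carries age.** The AE and SAE listings give arm and age for each event. SAP section 3 tabulates "number randomized by age group (<2 years" and older bands, with breaks at 8 and 13 years but none at 12.

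**The concern.** AEs and SAEs are the only outcome sections of the SAP without an age or formulation split, and no reason is given. Yet it is for AEs and SAEs that formulation and dose are most likely to matter. The pooled rate in each arm is a weighted average over two products and two dose levels, with weights set by the age mix that happens to be enrolled.

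The suspension group has its own open questions. Protocol 4.1.2 calls use below 2 years in Mexico, and use for respiratory infection, investigational. The dosage table in 4.1.1 gives a 3-day course, whereas this trial gives 5 days. Protocol 1.2.5 says there are no data in hospitalised patients with influenza or other ILI. Protocol 1.4.1 lists mainly gastrointestinal events among the most common AEs, and 8.2.1 requires new or worsening nausea, vomiting and diarrhoea to be reported.

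If the suspension had a tolerability problem, the planned table would show only a small difference between arms. The trial would then report no planned AE or SAE rate for that regimen.

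**Working it through.** **1. Does any planned output give the rate?**

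| Planned output | Split | Gives AE/SAE incidence under 12 years by arm? |
|---|---|---|
| AE and SAE tables (SAP 8, 9) | arm only | no |
| AE and SAE listings | arm and age per event | numerators only, by hand |
| Baseline age table (SAP 3) | breaks at 2, 8, 13, 18, 65 | denominators only, and none at 12 |
| Mortality, laboratory (SAP 7, 10) | 18 years | other outcomes; mixes suspension and tablet |
| Formulation subgroup (SAP 11) | 13 years | primary endpoint only |

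None does.

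**2. Inputs for the illustration**

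- Total N = 290, allocated 1:1 (protocol 3.4), so 145 per arm. The plan's figure is consistent: with the log-scale moments printed in the protocol 9.2 sample-size table (1.83/0.66 against 1.58/0.76), an unequal-variance t-test at two-sided 0.05 and 80% power gives 258. Then 258/0.90 = 286.7, or 287, which the plan sets at 290. This concern disputes none of it.
- Paediatric share s: the plan sets no quota. Protocol Table 2 has 253 of 1,376 aged 2 to under 12, so s = 253/1,376 = 0.184. That cohort starts at age 2 and the trial at 12 months, so s is an assumption, varied from 0.10 to 0.50.
- AE risks (assumed; the documents give none): 10% in every group except 30% on nitazoxanide suspension, a 20-point excess.

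**3. Group size.** Children per arm = 145 × 0.184 = 26.7.

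**4. Dilution.** Pooled excess = 20 × s if the harm is on suspension only, and 20 × (1 − s) if on tablets only. The 95% half-width in the under-12 stratum is 1.96 × √(0.10×0.90/n + 0.30×0.70/n), with n children per arm.

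| s | n per arm | Pooled excess, suspension-only harm | Pooled excess, tablet-only harm | Under-12 half-width |
|---|---|---|---|---|
| 0.10 | 14.5 | 2.0 points | 18.0 points | 28.2 points |
| 0.184 | 26.7 | 3.7 points | 16.3 points | 20.8 points |
| 0.30 | 43.5 | 6.0 points | 14.0 points | 16.3 points |
| 0.50 | 72.5 | 10.0 points | 10.0 points | 12.6 points |

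At s = 0.184 the expected counts are:

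- Pooled table: 145 × 0.10 = 14.5 on placebo, and 145 × (0.10 + 0.20 × 0.184) = 19.8 on nitazoxanide, that is 10.0% against 13.7%.
- Under-12 table: 26.7 × 0.10 = 2.7 against 26.7 × 0.30 = 8.0, that is 10% against 30%.

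**5. Would the SAP's under-18 subgroup do?** Ages 12 to 17 take the tablet. If they are a share t of all subjects (assumed), the under-18 excess is 20 × s/(s + t). That gives 15.7 points at t = 0.05 and 13.0 at t = 0.10. This is much better than pooling, but it still mixes the two regimens.

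**The case against.** The strongest reply is that this asks for extra output and does not correct an error.

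- **The stated objective is met.** The safety objective is AE, SAE and laboratory incidence, and it names no regimen. This stands, and it limits how much weight the point can carry.
- **Most of the information can be recovered.** Listings carry arm and age. The age table is for ITT, which the SAP defines as randomised and dosed, so it supplies dosed denominators by arm that miss the regimen cut only for 12-year-olds. This is true, but rates pieced together by hand are not a planned result.
- **Safety oversight does not rest on pooled tables.** The pausing rules count individual subjects, the protocol team reviews AEs at least twice monthly, and the DSMB reviews safety at least twice a year. This protects against unexpected severe events. It leaves open the final reporting of milder or expected AEs.
- **The scenario is assumed.** No document gives a 20-point excess, and at a 50% share the suspension group is not smaller at all. The same 100 to 200 mg twice-daily 5-day course was used in an earlier 100-subject trial at ages 1 to 11. The dose above the licensed level is the tablet, where dilution is slight. All of this is fair; the figures show how dilution works and do not predict harm.
- **The added tables would be imprecise.** At 27 per arm, 3 against 8 events gives a Fisher p-value of about 0.18, and cells by preferred term and grade would mostly hold 0 or 1. That argues against p-values, not against showing counts and denominators.

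**Conclusion.** The concern holds as an inexpensive reporting improvement. As written, the SAP gives no AE or SAE incidence for the under-12 suspension regimen, although the trial randomises within that stratum. That follows from the section headings and the subgroup rule and needs no assumption.

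The size of the dilution does rest on assumptions. At an 18.4% paediatric share and an assumed 10% against 30% on suspension, a 20-point excess shows as 3.7 points in the pooled table, with a range of 2.0 to 10.0 over shares of 10% to 50%. A tablet-only harm of the same size would still show as 16.3 points, so the gap concerns mainly the smaller group. The pooled safety objective and the efficacy analysis are unaffected.

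**What to change.** In SAP sections 8 and 9, keep the pooled ITT tables and repeat the subject-count tables (14.3.1.1 for AEs, 14.3.2.1 for SAEs) by arm within two strata: under 12 years (suspension) and 12 years and over (tablet). Use the number dosed per arm and stratum as the denominator, and give no p-values.

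Adding the existing age subgroups to the two headings would not be enough, because they split at 18. The 13-year formulation subgroup should not be used either, because the protocol's regimen and randomisation cut is 12.

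The cost is a few lines of SAP text and two repeated table shells. Arm, age and dosing are already collected, and neither sample size nor alpha changes. The drawback is small counts, about 27 children per arm under the assumed share with a half-width of about 21 points, so the tables should be labelled descriptive.
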